2 STUDY OBJECTIVES

2.1 Primary Objective

The primary objective of this study is to evaluate the efficacy of CSF-1 (0.4% pilocarpine hydrochloride ophthalmic solution) for the temporary correction of presbyopia.

2.2 Secondary Objectives

The secondary objectives of this study are to evaluate the safety and tolerability of CSF-1 (0.4% pilocarpine hydrochloride ophthalmic solution) versus Vehicle.

3 CLINICAL HYPOTHESES

The clinical hypothesis of this study is that CSF-1 is superior and/or safer/better tolerated compared with Vehicle for improving near vision in subjects with presbyopia.

4 OVERALL STUDY DESIGN

This is a 4-visit multi-center, randomized, double-masked, parallel-group study evaluating the safety and efficacy of CSF-1 compared with Vehicle in approximately 300 subjects with presbyopia. The study design is summarized in [Figure 1](#).

Visit 1 (Screening, Day -14 to -1): Qualified subjects will receive 1 drop of Vehicle instilled in each eye, followed by preliminary efficacy assessments to identify Vehicle responders at 15 minutes post-vehicle instillation.

Visit 2 (Day 1): Baseline assessments. Subjects who meet all inclusion and none of the exclusion criteria and qualify as Vehicle non-responders, will be randomized 1:1 to one of the following treatment arms:

- CSF-1 (0.4% pilocarpine hydrochloride ophthalmic solution)
- Vehicle

Pre-treatment measurements taken at this visit are considered as baseline.

At the Day 1 clinic visit, study personnel will instill Dose 1 of study drug at 8:30 AM \pm 30 minutes in each eye. Efficacy and safety assessments will be conducted for 2 hours following Dose 1. Dose 2 will be instilled by study personnel at 10:30 AM \pm 30 minutes in each eye. Efficacy and safety assessments will be conducted for 4 hours following Dose 2.

[figure not shown]
All subjects will be instructed to dose twice daily (BID) with a single drop for approximately 1 week in each eye. The first daily dose should occur in the morning, with the second dose following 2 hours later (+1 hour). Subjects will be instructed not to dose at home on clinic visit days.

Visit 3 (Day 8): Study personnel will instill Dose 1 of study drug at 8:30 AM \pm 30 minutes in each eye. Efficacy and safety assessments will be conducted for 2 hours following Dose 1. Dose 2 will be instilled by study personnel at 10:30 AM \pm 30 minutes in each eye. Efficacy and safety assessments will be conducted for 2 hours following Dose 2.

All subjects will be instructed to dose twice daily (BID) with a single drop for approximately 1 week in each eye. The first daily dose should occur in the morning with the second dose following 3 hours later (+1 hour). Subjects will be instructed not to dose at home on clinic visit days.

Visit 4 (Day 15): Study personnel will instill Dose 1 of study drug at 8:30 AM \pm 30 minutes in each eye. Efficacy and safety assessments will be conducted up to 3 hours following Dose 1. Dose 2 will be instilled by study personnel at 11:30 AM \pm 30 minutes in each eye. Efficacy and safety assessments will be conducted for 5 hours following Dose 2.

Figure 1: Study Design

5 STUDY POPULATION

Approximately, 300 healthy adult subjects (2 arms; 150 subjects per treatment arm) will be enrolled between 45 and 64 years of age with presbyopia who also meet the following criteria.

5.1 Inclusion Criteria

Subjects must:

1. Be able and willing to provide written informed consent and sign a Health Information Portability and Accountability Act (HIPAA) form prior to any study procedure being performed;
2. Be able and willing to follow all instructions and attend study visits;
3. Be 45 to 64 years of age of either sex and any race or ethnicity at Visit 1;
4. [REDACTED]
5. [REDACTED]
6. [REDACTED]
7. [REDACTED]
8. Have a negative urine pregnancy test at Visit 1, if female of childbearing potential (those who have experienced menarche and who are not surgically sterilized [bilateral tubal ligation, hysterectomy, or bilateral oophorectomy] or post-menopausal [12 months after last menses]) and must use adequate birth control throughout the study period. Adequate birth control is defined as hormonal – oral, implantable, injectable, or transdermal contraceptives; mechanical – spermicide in conjunction with a barrier such as condom or diaphragm; intrauterine device (IUD); or surgical sterilization of partner. For non-sexually active females, abstinence may be regarded as an adequate method of birth control;
9. Be able and willing to avoid all prohibited medications for the appropriate washout periods and during the study without significant risk to the subject.

5.2 Exclusion Criteria

Subjects must not:

1. Be a female of childbearing potential who is currently pregnant, nursing, or planning a pregnancy;
2. Have known contraindications or a sensitivity to the use of any of the study drugs or their components;
3. Have an active ocular infection at Visit 1 (bacterial, viral, or fungal);
4. Have active ocular inflammation (e.g., moderate to severe blepharitis, any allergic conjunctivitis, peripheral ulcerative keratitis or scleritis) in either eye at Visit 1;

5. Have a known history or diagnosis of ocular herpetic infection, iritis, scleritis, or uveitis in either eye, whether active or inactive;
6. [REDACTED]
7. Be unable to or refuse to discontinue soft contact lens wear 7 days prior to study Visit 1 and rigid gas permeable (RGP) contact lens wear 14 days prior to Visit 1 and for the duration of the study;
8. Have moderate or severe dry eye defined as total corneal fluorescein staining > 2 ([REDACTED] Scale) in either eye at Visit 1 and/or use artificial tears or lubricant eye ointment on a daily basis;
9. Plan to use artificial tears or lubricant eye ointment on the day of or during any study visits;
10. Have clinically significant abnormal lens findings (e.g., cataract) in either eye at Visit 1;
11. [REDACTED]
12. Have an average dark-adapted pupillometry measurement of < 3.5 mm in either eye at Visit 1;
13. Have intraocular pressure (IOP) that is < 9 millimeters of mercury (mmHg) or > 22 mmHg in either eye at Visit 1, or have a prior diagnosis of ocular hypertension or glaucoma or be currently being treated with any type of topical IOP-lowering (glaucoma) medication at Visit 1;
14. Have clinically significant abnormal findings (e.g., central corneal scar) on a slit lamp biomicroscopy exam in either eye documented at Visit 1 or a known history of a clinically significant slit-lamp finding in either eye;
15. Have clinically significant abnormal findings on a dilated indirect ophthalmoscopy exam in either eye documented at Visit 1 or a known history of a clinically significant retinal finding in either eye;
16. Have had ocular surgical intervention within 6 months prior to Visit 1, or planned surgical intervention within 30 days after Visit 4;
17. Use any of the following prohibited systemic medications during the timeframe noted below:
 - a. The day of the study visit or within 12 hours prior to a study visit (chronic, daily use is not allowed):
 - i. nonsteroidal anti-inflammatory drugs (NSAIDs) (e.g., Advil[®], Motrin[®])
 - ii. narcotic (opiate class) pain medication (e.g., codeine, OxyContin[®], Vicodin[®], Tramadol[®])
 - b. Two (2) weeks (14 days) prior to Visit 1 or for the duration of the study:
 - i. bladder medication (e.g., Urecholine[®], bethanechol)

- ii. antipsychotics
 - iii. antidepressants
 - iv. attention-deficit/hyperactivity disorder (ADHD) medications
 - v. alpha-blockers (e.g., tamsulosin [Flomax®], Jayln®, Uroxatral®, Rapaflo®)
 - vi. anticholinergics (e.g., atropine, belladonna, benztropine, dicyclomine, donepezil, hyoscyamine, propantheline, scopolamine, trihexphenidyl)
 - vii. muscarinic receptor agonists or cholinergic agonists (e.g., Salagen®, Evoxac®) other than the study drug
 - viii. over-the-counter (OTC) or prescription antihistamines or decongestants
 - ix. any ophthalmic medications (other than artificial tears or lubricant eye ointment [see exclusion 8 and 9 above])
 - x. any other medication affecting the pupil or accommodation
 - xi. recreational drug use (e.g., marijuana, methadone, heroin, cocaine)
18. Have a diagnosis of diabetes mellitus or a history of elevated blood sugar;
19. Have a condition or a situation that in the investigator's opinion may put the subject at increased risk, confound study data, or interfere significantly with the subject's study participation, including but not limited to unstable cardiovascular, hepatic, renal, respiratory, gastrointestinal, endocrine, immunologic, dermatologic, hematologic, neurologic, or psychiatric disease.

5.3 Withdrawal Criteria

A subject may withdraw consent to participate in the study at any time for any reason. Subjects will be withdrawn from the study if any of the following criteria are met:

- Be a female of childbearing potential who is currently pregnant, nursing, or planning a pregnancy; tests positive to a urine pregnancy test at Visit 4; or refuses to use an adequate method of contraception for the duration of the study;
- Have an active ocular infection (bacterial, viral, or fungal), active ocular inflammation (e.g., moderate to severe blepharitis, allergic conjunctivitis, peripheral ulcerative keratitis, scleritis, uveitis) at Visit 2, Visit 3, or Visit 4 in either eye.
- Subjects may also be withdrawn from the study for the following reasons:
 - Adverse Event (AE)
 - Lost to follow-up
 - Death
 - Subject not adequately following required study procedures
 - Study terminated by the Sponsor
 - Other

Subject withdrawals will be documented on the subjects' source document.

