8.6 Subject Disposition

Completed Subjects

A completed subject is one who has not been discontinued from the study and successfully completes all 4 study visits.

Withdrawn Subjects

A subject may be withdrawn for meeting any of the withdrawal criteria as described in Section [5.3](#).

Discontinued Subjects

A discontinued subject is one who does not complete the protocol-defined study visits. A subject may be discontinued at the discretion of the investigator, sponsor, and/or the Institutional Review

Board (IRB). Notification of early discontinuation from the study and the reason for discontinuation will be made to the sponsor and/or [REDACTED]

Prior to discontinuing a subject, every effort should be made to obtain as much follow-up data as possible, and to retrieve all study materials. AEs will be followed as described in [Section 9](#).

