10.7 Efficacy Analysis

Primary Efficacy Analyses

The primary efficacy endpoint in this study is the percentage of subjects with a ≥ 3 -line (15-letter) gain, from baseline, in best distance-corrected visual acuity (BDCVA) at 40 cm (Precision Vision chart) and no loss in best distance corrected visual acuity ≥ 5 letters (ETDRS chart) at Visit 3, 1 hour following Dose 1 in the study eye. The primary efficacy analysis will be conducted in the FAS with intercurrent events handled in the following manners:

- 1) Discontinuation of study drug and non-optimal compliance will be ignored [treatment policy strategy].
- 2) Withdrawal due to lack of efficacy or adverse events: missing data will be singly imputed as failure [hypothetical strategy].
- 3) Missing data without withdrawal or withdrawal due to reasons other than lack of efficacy or adverse events: missing data will be imputed employing Multiple Imputation (MI) using randomized treatment-based Markov Chain Monte Carlo (MCMC) methodology [hypothetical strategy].

No subject data will be excluded from the FAS due to protocol violations/deviations. The FAS will be used for the primary efficacy analyses. Note that multiple imputations of missing values will be completed for the continuous measures (BDCVA at 40 cm and best distance corrected VA at 4m), then the response variable will be determined therefrom.

[REDACTED]

Descriptive statistics will be presented by treatment group. Testing of the percentage of subjects with at least a 3-line (15-letter) improvement from baseline in BDCVA at 40 cm without a loss of ≥ 5 letters in best distance corrected VA at 4m will be completed separately for the 1 hour and 2 hour time points using a generalized linear mixed model with a binomial distribution including fixed effects of baseline BDCVA at 40 cm as a covariate, daily dose (Dose 1 and Dose 2), treatment, and the interaction of dose with treatment and random effect of subject to account for the correlation within a subject between daily doses. [REDACTED]

[REDACTED]

The adjusted odds ratios and marginal proportions and difference in proportions along with corresponding two-sided 95% Confidence Intervals (CIs) and p-values will be presented.

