8.5 Adjustment for Multiplicity

If the primary null hypothesis, H_{01} , is rejected at a 2-sided alpha = 0.05 in favor of CSF-1 in the alternative hypothesis, H_{11} , tested as delineated in the primary efficacy analysis section ([Section 12.1](#)), then the study will be considered a success and the following key secondary hypotheses will be tested in hierarchical order, each at a 2-sided alpha = 0.05, where inference will be made on each null hypothesis only if the prior null hypotheses are rejected in favor of CSF-1.

1. Visit 3 (Day 8), 2 hours following Dose 1 (H_{02})
2. Visit 3 (Day 8), 1 hour following Dose 2 (H_{03})
3. Visit 3 (Day 8), 2 hours following Dose 2 (H_{04})

9. Disposition of Subjects

Subject disposition will be presented in terms of the numbers and percentages of subjects who were randomized, completed the study, and discontinued from the study. A discontinued subject is someone who does not complete the 4 protocol-defined study visits. Subjects who are not discontinued from the study will be considered study completers. Disposition will be summarized by treatment arm for all randomized subjects. The reasons for study discontinuation will also be summarized and include: AE, lost to follow-up, physician decision, protocol violation, study terminated by sponsor, withdrawal by subject, death, and other. A subject listing will be provided which includes the date and reason for study discontinuation.

The number of subjects in each of the analysis sets (FAS, PPS, and SAF) will be displayed by treatment arm, with the number of subjects and percentages calculated using randomized subjects as the denominator. The number and percentage of subjects with any (major, or minor) protocol deviations will be summarized by treatment arm and overall for all randomized subjects. Protocol deviations will be classified as major or minor prior to the closure of the database during a masked review of each protocol deviation. Major deviations will be defined as those deviations that potentially affect the analysis of the primary study endpoint.

A subject listing will be provided which includes the date of the deviation, the deviation code and description, and the classification of whether the deviation was deemed major or minor. In addition, subject listings will include treatment arm and ICF signature date, and exclusions from the PPS. There will also be a listing of screen failures.

10. Demographic and Baseline Characteristics

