12.1 Primary and Key Secondary Efficacy Analysis

The primary efficacy endpoint in this study is the percentage of subjects with a ≥ 3 -line (15-letter) gain, from baseline, in best distance-corrected visual acuity (BDCVA) at 40 cm (Precision Vision chart) and no loss in BDCVA ≥ 5 letters (ETDRS chart) at Visit 3, 1 hour following Dose 1 in the study eye. The key secondary efficacy endpoints are defined the same as the primary efficacy endpoint, except for being measured at 2 hours following Dose 1, 1 hour following Dose 2, and 2 hours following Dose 2, all at Visit 3.

The primary and key secondary efficacy analysis will be conducted in the FAS with missing data handled in the following manners:

1. Discontinuation of study drug and non-optimal compliance will be ignored [treatment policy strategy].
2. Withdrawal due to lack of efficacy or AEs: missing data will be singly imputed as failure [hypothetical strategy].
3. Missing data without withdrawal or withdrawal due to reasons other than lack of efficacy or AEs: missing data will be imputed employing Multiple Imputation (MI) using randomized treatment-based Markov Chain Monte Carlo (MCMC) methods.

No subject data will be excluded from the FAS due to protocol violations/deviations. The multiple imputation of missing values will be completed for the continuous measures (BDCVA at 40 cm and BDCVA at 4 m), then the response variable will be determined therefrom. Imputation of failure due to lack of efficacy or AE will be assigned after multiple imputation is performed.

Variables for treatment group, baseline for BDCVA at 40 cm and baseline for BDCVA at 4 m will also be included in the multiple imputation model. 25 complete imputed datasets will be created.

Example SAS® code for the multiple imputation:

```
PROC MI DATA=DATAIN OUT=MI NIMPUTE=25 SEED=118787 minimum=-0.3 maximum=1;
  MCMC INITIAL=EM;
  VAR TRTPN VA40 VA40BL VA4 VA4BL;
RUN;
```

Where TRTPN = treatment group, coded 1 for CSF-1, else 0

VA40 = value of BDCVA at 40 cm for Visit 3, 1 hour after Dose 1

VA40BL = baseline value of BDCVA at 40 cm

VA4 = value of BDCVA at 4 m for Visit 3, 1 hour after Dose 1

VA4BL = baseline value of BDCVA at 4 m

For each imputed dataset, a logistic regression model with baseline BDCVA at 40 cm as a covariate and treatment as a main effect will be used to obtain the treatment effect estimate, odds ratio, and 95% confidence interval (CI) for odds ratio.

Example SAS® code for the logistic model is shown here:

```

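### Withdrawal for poor procedure-following can leave Visit 3 acuity unmeasured in subjects whose non-compliance the primary analysis says it will ignore

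*Protocol*

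**What the plan says.** **Conduct.** Protocol 5.3 has a mandatory list of withdrawal criteria and then a permissive one, introduced by "Subjects may also be withdrawn from the study for the following reasons". The permissive list includes "Subject not adequately following required study procedures". Protocol 8.6 adds: "A subject may be discontinued at the discretion of the investigator, sponsor" (the IRB is also named). SAP Section 9 tabulates these reasons for study discontinuation: "AE, lost to follow-up, physician decision, protocol violation, study terminated by sponsor, withdrawal by subject, death, and other". Neither list contains lack of efficacy. Section 8.6 also asks that every effort be made to collect follow-up data before a subject is discontinued.

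**Analysis.** Rule 1 of the primary analysis reads "Discontinuation of study drug and non-optimal compliance will be ignored [treatment policy strategy". SAP 12.1, like Protocol 10.7, adds "No subject data will be excluded from the FAS due to protocol violations/deviations". Rule 2 imputes failure after withdrawal for lack of efficacy or an adverse event. Rule 3 covers missing data without withdrawal and "withdrawal due to reasons other than lack of efficacy or adverse events: missing data will be imputed employing Multiple Imputation (MI". Protocol 10.7 and 10.10 label rule 3 a hypothetical strategy; SAP 12.1 keeps the method without the label. The SAP's example imputation code contains treatment, the two Visit 3 acuities and their two baselines.

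**Timing.** Under the Protocol's Subject Instructions (7.1), the first-week diary is kept until Visit 3, and used vials are returned at the next visit for a compliance check. At Visit 3 staff instill both doses. The primary reading is 1 hour after Dose 1, and all three key secondary readings are later the same day.

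**The concern.** A treatment policy strategy for non-compliance works only if the outcome is measured in non-compliant subjects. The conduct sections allow a site or the sponsor to end study participation for that same behaviour. A subject who skipped home doses and stays is analysed as observed under rule 1. An identical subject who is withdrawn before the 1-hour reading is still in the FAS but is imputed under rule 3. A discretionary decision then determines which strategy applies.

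Rule 2 may not catch these cases. A subject who neglected the drops because they did not help has no lack-of-efficacy category to be recorded under, whereas a non-compliance category is available. The imputation code has no term for compliance or reason for withdrawal, and it does not use the subject's own Day 1 post-dose acuity. Such a subject would be imputed much like anyone in the arm with similar baselines. At stake are the primary endpoint and the three key secondary endpoints, all measured at Visit 3.

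**Working it through.** **1. When the outcome is lost.** The visible text describes no scheduled contact between Day 1 and Day 8, so home non-compliance would normally come to light at Visit 3.
- Withdrawal before the 1-hour reading (at the Visit 3 compliance check, or earlier on self-report) loses the primary and all three key secondary outcomes.
- Withdrawal between the 1-hour reading and the end of Visit 3 keeps the primary outcome and loses some key secondary outcomes.
- Withdrawal after Visit 3 loses none of the four.

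The visible text does not say whether the compliance check precedes Dose 1; the visit procedures are redacted.

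**2. The plan's own figures.** Inputs from Protocol 10.5: 42.5% and 17.5%, 140 per arm, two-sided 0.05, about 5% discontinuation, about 150 randomized per arm.
- Pooled standard error: √(2 × 0.30 × 0.70 / 140) = 0.0548. Unpooled: √((0.425 × 0.575 + 0.175 × 0.825) / 140) = 0.0527.
- Power = Φ((0.25 − 1.96 × 0.0548) / 0.0527) = Φ(2.71) = 99.66%, consistent with the stated bound of more than 97.5%.
- 140 / 0.95 = 147.4, rounded up to 148, consistent with about 150.

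**3. Size of the distortion.** Let f be the share of CSF-1 subjects withdrawn on this ground before the reading, and r their unmeasured response rate. Neither is in the documents. The imputed result is approximated by the arm's planned rate. This is a simplification, because the SAP imputes acuity given arm and baselines and then dichotomises.

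Treatment-policy CSF-1 rate = (1 − f) × 42.5% + f × r, so overstatement = f × (42.5% − r).

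| f | r = 42.5% | r = 17.5% | r = 0 |
|---|---|---|---|
| 1% | 0 | 0.25 points | 0.43 points |
| 2% | 0 | 0.50 | 0.85 |
| 2.5% (half the planned loss) | 0 | 0.63 | 1.06 |
| 5% (all the planned loss, 7.5 of 150) | 0 | 1.25 | 2.13 |
| 10% (twice the planned loss) | 0 | 2.50 | 4.25 |

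With 5% lost in both arms and r = 0 in both, the rates are 0.95 × 42.5 = 40.4% and 0.95 × 17.5 = 16.6%. The difference is 23.75 points, so the planned 25 is overstated by 1.25.

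**4. Power at 150 per arm.** With no loss: 99.8%. With f = 5% in CSF-1 only, using the treatment-policy rate: 99.6% (r = 17.5%) or 99.4% (r = 0). With 5% lost in both arms and all counted as failures: 99.6%.

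**5. Cover from SAP 12.2.** Missing-as-failure reproduces the r = 0 case. The tipping point analysis starts from the worst case, with missing CSF-1 subjects as failures and missing Vehicle subjects as successes. With 5% missing per arm that gives 40.4% against 0.95 × 17.5 + 5 = 21.6%, and power of 94.3%. The two observed-data analyses (FAS and PPS) omit these subjects and do not address the point.

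**The case against.** The strongest defence has five parts.

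- **The plan is openly mixed.** Rule 1 covers compliance while in the study, and rule 3 covers study withdrawal under a declared hypothetical strategy. This stands. A reader might infer that the treatment-policy estimand is simply not delivered; the documents do not support that. The gap is that the same behaviour can fall under either rule.
- **Loss is conditional.** Withdrawal is optional, and compliance is normally first checked at Visit 3. This stands. A reader might infer that the Visit 3 response of a poorly compliant subject is never measured; that is true only if withdrawal precedes the reading.
- **Direction is unknown.** The endpoint follows a staff-instilled dose, and nothing in the documents shows that missed home drops lower the response to it. This stands. A reader might infer that the CSF-1 rate necessarily moves up; that is an assumption, and r = 0 lies below even the planned Vehicle rate. The same fact shows the loss is avoidable, since missed home doses do not prevent a Visit 3 measurement.
- **Some cases belong under rule 2.** Withdrawal because of stinging can be recorded as an adverse event and imputed as failure. This stands for intolerance, not for perceived lack of benefit.
- **Safeguards exist.** The every-effort text in 8.6 and two of the four sensitivity analyses help. They are partial: 8.6 does not name Visit 3 acuity, and the sensitivity analyses bound the effect without recovering the data.

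The visit procedures are redacted and the appendix content is not shown, so a provision for continued measurement may exist there.

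**Conclusion.** The inconsistency is real and modest. Protocol 5.3 and 8.6 allow study withdrawal for behaviour that Protocol 10.7, 10.10 and SAP 12.1 say will be ignored, with no visible provision for measuring Visit 3 acuity in those subjects.

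The figures of 1.25 to 2.1 points are upper-end illustrations. They assign the whole 5% discontinuation allowance, which covers all reasons, to this one ground, before the reading, in CSF-1 only. Similar losses in both arms with no responders give 1.25 points in the difference; half the CSF-1 loss gives 0.6 to 1.1 points; no link between compliance and response gives zero. Power stays above 99% in each of these scenarios, and is 94.3% at the tipping point worst case. The trial's conclusion is not threatened. This is a cheap improvement that reduces avoidable missing primary data.

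A reader might also infer that the withdrawal criterion must be deleted, discretion curtailed, or protocol violation dropped from SAP Section 9. None of these is needed, and dropping the reporting category would only make such losses harder to see.

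**What to change.** Reconcile Protocol 5.3 and 8.6 with Protocol 10.7, 10.10 and SAP 12.1 by separating non-compliance, or stopping study drug, from the end of data collection:

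1. State that non-compliance alone is recorded as a deviation, for which the PPS (SAP 7.2) already provides.
2. State that any such subject who still consents has 40 cm and 4 m BDCVA measured at the scheduled Visit 3 times whether or not dosing continues, and that these values enter the FAS analysis under rule 1.

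Leave safety withdrawals, the right to withdraw consent, clinical discretion over dosing and the SAP Section 9 reporting categories as they are. This changes what is measured, not how any subject is treated.

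The cost is a few sentences in the protocol and a matching line in the SAP, with no new visits or assessments. The small downside is that the CSF-1 responder rate may be slightly lower once these subjects are measured.
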